## 12.2 Interim analyses

We will monitor major adverse event rates as described above, in particular serious bleeding complications (hemorrhage Grade 3 or 4, as defined by CTCAE v4.0). We will monitor and estimate the incidence rate of serious bleeding in study participants, and report all occurrences and corresponding analytic summaries (such as the estimated incidence rate with 95% confidence intervals) to the DSMB to assist in decision-making regarding early termination for safety.

Allogeneic HCT is an intensive therapy with many associated side effects and toxicities related to the transplant conditioning regimen; the ensuing immunosuppressed status; adverse effects of standard post-transplant medications; and graft-vs-host interactions or GvHD. Toxicities, including Grade 4 toxicities, are relatively common. Non-relapse mortality (NRM) is a definitive endpoint which captures fatal effects of any aspect of the transplant process outside of disease relapse, and thus represents the most accurate and reproducible measure of the toxicity and safety of the allogeneic HCT process.

The baseline cumulative incidence of NRM after allogeneic HCT for acute leukemia with FLU/MEL conditioning was estimated in a recent large cohort study at 20% (22). In order to ensure that patients are not harmed by the study intervention, the formal stopping rule below monitors that the study intervention does not increase the risk of NRM in participants.

The stopping rule is based on the incidence of NRM at 1 year after allogeneic HCT. Patients will be evaluable with regard to the stopping rule if they die or if they reach 1 year post-transplant, whichever occurs first. The stopping rule will be tested every increment of 5 evaluable patients. The stopping rule will be triggered if any of the following conditions are met:

Number of evaluable patients	Number of patients with NRM
5	3
10	5
15	6
20	8
25	9
30	10
35	12
40	13

If the stopping rule is triggered, the study will be terminated, and FDA so notified. This stopping rule provides 80% power to detect an increase in NRM with a type I error rate of 0.05. The stopping rule was constructed using the Pocock boundary with the same significance level for all looks at the data. The rule was created using R v.3.1.3 and the clinfun package.

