### Antiplatelet Agents and Anticoagulants

Fatal bleeding events have occurred in subjects treated with ibrutinib. Grade 3 or higher bleeding events (subdural hematoma, gastrointestinal bleeding, hematuria and post procedural hemorrhage) have occurred in up to 6% of subjects. Bleeding events of

any grade, including bruising and petechiae, occurred in approximately half of subjects treated with ibrutinib. The mechanism for the bleeding events is not well understood.

Ibrutinib may increase the risk of hemorrhage in subjects receiving antiplatelet or anticoagulant therapies. See Section 6 (Dose Modification) for recommendations regarding ibrutinib dosing in subjects undergoing surgery or other invasive procedures.

Warfarin or vitamin K antagonists should not be administered concomitantly with ibrutinib. Supplements such as fish oil and vitamin E preparations should be avoided. Use ibrutinib with caution in subjects requiring other anticoagulants or medications that inhibit platelet function. Subjects with congenital bleeding diathesis have not been studied. Ibrutinib should be held at least 3 to 7 days pre- and post-surgery depending upon the type of surgery and the risk of bleeding.

Subjects requiring the initiation of therapeutic anticoagulation therapy (other than warfarin or a vitamin K antagonist) during the course of the study should have treatment with ibrutinib held, and ibrutinib should not be restarted until the subject is clinically stable and has no signs of bleeding. Subjects should be observed closely for signs and symptoms of bleeding. No dose reduction is required when study drug is restarted.

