## **2) All serious and unexpected toxicities**

Defined as those toxicities not identified in the transplant literature, product inserts, or study consent form.

The following will be *recorded*, but generally will **not** be *reported* as AEs or SAEs, unless also considered related to the study drug.

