### **3) Common and expected toxicities of HCT $\leq$ Grade 4 that are well-described in transplant literature, the product inserts, or study consent form and do not result in death.**

In general, these toxicities are considered reversible. The specific reporting requirements are found in the protocol. These Grade 4 toxicities include, but are not limited to, alopecia, anemia, anorexia, bleeding requiring transfusions, cardiac arrhythmias, central venous catheter infections, constipation, diarrhea, edema, fatigue, febrile episodes, gastritis, graft failure, graft versus host disease, hematuria, hypertension, hypotension, hypoxia, incontinence, infections, insomnia, laboratory abnormalities, mental status changes, mood alterations, mucositis, nausea, neutropenia, pain, pleural effusion, pneumonitis, rash, seizures, sepsis, sinusoidal obstructive syndrome, tachycardia, thrombocytopenia, thrombotic microangiopathy, tremor, vomiting. For IND studies, SAEs that are SUSARs per 21CFR§312.32 will be reported as IND Safety Reports (see above).

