### **Major Hemorrhage**

Major hemorrhage is defined as any of the following:

- Any treatment-emergent hemorrhagic adverse events of Grade 3 or higher\*. Any treatment-emergent serious adverse events of bleeding of any grade
- Any treatment-emergent central nervous system hemorrhage/hematoma of any grade

\*All hemorrhagic events requiring transfusion of red blood cells should be reported as Grade 3 or higher AE per CTCAE v4.0.

Events meeting the definition of major hemorrhage will be captured as an event of special interest.

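### The bleeding rate that Section 12.2 sends to the DSMB counts only Grade 3 or 4 hemorrhage, so fatal bleeds and low-grade CNS or serious bleeds fall outside its numerator

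*Combined protocol and SAP*

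**What the plan says.** Section 12.2 (Interim analyses) commits to monitoring major adverse event rates and singles out serious bleeding, defined as "hemorrhage Grade 3 or 4, as defined by CTCAE v4.0". The investigators will "report all occurrences and corresponding analytic summaries (such as the estimated incidence rate with 95% confidence intervals) to the DSMB", to support decisions on stopping early for safety. No numerical bleeding boundary is given. The only formal stopping rule in that section is on NRM at 1 year.

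Two other places describe serious bleeding more widely.

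- Section 7.2, Adverse Events of Special Interest, Major Hemorrhage, has three limbs: hemorrhage of Grade 3 or higher, serious bleeding of any grade, and "Any treatment-emergent central nervous system hemorrhage/hematoma of any grade". These events go to the manufacturer's drug safety unit; the DSMB is not named there.
- Section 4.1, Antiplatelet Agents and Anticoagulants, gives a background rate of up to 6% for Grade 3 or higher bleeding and states: "Fatal bleeding events have occurred in subjects treated with ibrutinib".

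Section 7.2 also speaks twice about bleeding that needs transfusion. The footnote to Major Hemorrhage says: "All hemorrhagic events requiring transfusion of red blood cells should be reported as Grade 3 or higher AE per CTCAE v4.0". The list of common and expected transplant toxicities includes "anorexia, bleeding requiring transfusions, cardiac arrhythmias", and that list belongs to a group of events that are recorded but generally not reported "as AEs or SAEs, unless also considered related to the study drug".

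**The concern.** On the CTCAE scale a death due to an event is Grade 5. A definition that stops at Grade 4 therefore removes the worst outcome from the one bleeding statistic the plan prepares for a termination decision. It also removes intracranial bleeds graded 1 or 2, which the protocol elsewhere treats as major at any grade, and serious bleeds of low grade.

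Three things are at stake. The reported rate and interval can be too low. The rate is not like-for-like with the protocol's own background figure, and the mismatch favours the drug. The manufacturer would also be working from a wider bleeding definition than the DSMB's summary uses.

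Separately, the two Section 7.2 statements on transfused bleeding give sites different reporting instructions. One applies to every such hemorrhage; the other turns on whether the event is judged drug-related, which is hard to judge in a single-arm trial.

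**Working it through.** **Step 1. Compare the definitions.**

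| Event | In the Section 12.2 rate? | Major hemorrhage in Section 7.2? |
|---|---|---|
| Grade 3 or 4 bleed | Yes | Yes |
| Fatal (Grade 5) bleed | No | Yes (Grade 3 or higher) |
| Grade 1-2 CNS bleed | No | Yes (CNS limb) |
| Serious Grade 1-2 bleed outside the CNS | No | Yes (serious limb) |

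**Step 2. See what other routes catch.**

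- Deaths (Section 7.2): non-relapse deaths on treatment, within 90 days of the last dose, or later if treatment-related, are reported individually to the safety board.
- Serious events of Grade 3 and above (Section 7.2) go to the DSMC regardless of relatedness.
- The NRM rule (Section 12.2) counts non-relapse deaths from all causes together, up to 1 year after transplant.
- Non-fatal Grade 1-2 CNS or serious bleeds fall below the Grade 3 limit of the DSMC route and are not deaths.

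The Synopsis and Section 4.2 continue treatment to 18 months after transplant. A fatal bleed between 12 and 18 months is then in neither the bleeding rate nor the NRM rule, although it would be reported as a death. Section 5.1 instead gives a treatment duration of 1 year. From a start at Day +60 to Day +90 that ends at Day 60 + 365 = 425 to 90 + 365 = 455, still beyond the 1-year NRM window.

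**Step 3. Illustrate the size.** The plan states no expected bleeding rate or boundary for the DSMB summary, so there is no figure to reproduce.

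Inputs: n = 45 treated, which Section 12.1 assumes out of 50 enrolled. Section 7.2 defines adverse events as arising after ibrutinib is received, so treated subjects are the natural denominator; n = 50 is shown as the other end of the range. The background rate is up to 6% (Section 4.1). The event counts are assumptions.

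Expected Grade 3 or higher bleeds at 6%: 45 × 0.06 = 2.7, or 50 × 0.06 = 3.0.

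The exact (Clopper-Pearson) interval for x events in n has lower limit B(0.025; x, n − x + 1) and upper limit B(0.975; x + 1, n − x), where B is the beta quantile.

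| Assumed events | n = 45 | n = 50 |
|---|---|---|
| Three Grade 3 or higher, all counted | 3/45 = 6.7% (1.4-18.3) | 3/50 = 6.0% (1.3-16.5) |
| Same three, one fatal, rate as written | 2/45 = 4.4% (0.5-15.1) | 2/50 = 4.0% (0.5-13.7) |

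Each omitted event moves the rate by 1/45 = 2.2 percentage points. With about three events expected, one omission removes about a third of the count.

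**Step 4. How likely is an omission?** If the excluded event types have a combined true rate f, the chance of at least one among 45 is 1 − (1 − f)^45. This gives 20% for f = 0.5%, 36% for f = 1% and 60% for f = 2%. The documents give no value for f; these are a range only.

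**The case against.** The strongest reply is that the DSMB is not blind to these bleeds. Fatal ones arrive as individual death reports, including after the NRM window closes, and Grade 3 or higher serious events go to the DSMC whatever their attribution. Section 12.2 promises all occurrences as well as a rate, and no decision rule is tied to that rate. The two intervals in the illustration overlap almost entirely. The wider definition in Section 7.2 was written for reporting to the manufacturer, and nothing obliges the DSMB summary to adopt it. Finally, Section 7.2 refers to deaths from Grade 4 toxicities, so staff might tally a fatal bleed as Grade 4.

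Much of this stands and limits the point. A reader might infer that fatal bleeds escape the DSMB. The documents do not support that: they leave the bleeding rate, not oversight. What the reply does not do is repair the rate. The NRM rule pools all causes of death and stops at 1 year, and the promise of all occurrences is attached to the same Grade 3 or 4 definition. That staff might grade a fatal bleed either way is a reason to settle the wording.

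A reader might also infer that Section 7.2 exempts transfused bleeding from reporting, and that the DSMB's estimate therefore depends on attribution. That goes too far. The list says only that such events are generally not reported, and it excepts drug-related and fatal events. Events that cause or prolong hospitalization stay serious adverse events, all adverse events are recorded, and Section 12.2 sets no relatedness condition. Attribution could reach the rate only if it were compiled from submitted reports rather than recorded events, which the protocol does not say.

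**Conclusion.** The point holds for the bleeding rate and its confidence interval. Taken literally, the Section 12.2 definition omits fatal bleeds, Grade 1-2 CNS bleeds and serious Grade 1-2 bleeds, and it conflicts with the protocol's own major-hemorrhage definition and with the grade range of its background figure. The case for including fatal bleeds is the firmest. Adding the low-grade CNS and serious bleeds rests on the protocol already calling them major.

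The size is a few percentage points for each event or two omitted. It rests on assumed counts, an assumed fatal share and about 45 treated subjects, and no boundary exists that the difference could cross. The treatment of transfused bleeding in Section 7.2 is an unreconciled contradiction, not an exemption. This should be corrected, but it does not mean that safety oversight is missing.

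**What to change.** - In Section 12.2, replace the Grade 3 or 4 limit with Grade 3 or higher, including Grade 5. Preferably, define the monitored event by the major-hemorrhage definition already in Section 7.2.
- Show fatal bleeds and CNS bleeds on separate lines in the DSMB summary, and state the denominator (subjects who received at least one dose of ibrutinib).
- Reconcile the Section 7.2 list of expected transplant toxicities with the Major Hemorrhage footnote, for example by stating that events meeting the major-hemorrhage definition are outside that list.

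The cost is wording only. These events are already captured as events of special interest, so no new data are needed. The one drawback is that the reported bleeding rate may look slightly less favourable.

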Serious adverse events (SAEs) CTCAE Grade 3 and above, and all subsequent follow-up reports will be reported to the Stanford Cancer Center Data and Safety Monitoring Committee (DSMC) using the study specific CRF regardless of the event's relatedness to the investigation. Following review by the DSMC, events meeting the IRB definition of 'Unanticipated Problem' will be reported to the IRB using eProtocol within 10 working days of DSMC review, or within 5 working days for deaths or life-threatening experiences. If complete information is not available at the time, the investigator must provide follow-up information as soon as it is known.

Adverse events that are serious and unexpected suspected adverse reactions, and are possibly, probably, or definitely related to the study drug ibrutinib (SUSAR per 21CFR§312.32), will be reported to the FDA via IND Safety Report [21CFR§312.32]

within 14 calendar days, or within 7 calendar days if the event is an unexpected fatal or life-threatening suspected adverse reaction.

In addition, all serious adverse events (initial and follow-up information) will be reported on the Serious Adverse Event Report Form from Pharmacyclics and sent via email or fax to Pharmacyclics Drug Safety or designee within 24 hours of the discovery of the event or information. Pharmacyclics may request follow-up and other additional information from the Investigator (for instance, hospital admission/discharge notes and laboratory results). The contact information (phone, email and fax) for Pharmacyclics Drug Safety can be found on the Serious Adverse Event Report Form and instructions.

Hematopoietic cell transplantation (HCT) is an aggressive therapy for the treatment of a number of life-threatening malignant and non-malignant disorders. Individuals considered for HCT have generally exhausted other avenues of effective therapy. The non-relapse mortality (NRM) associated with a sibling-donor myeloablative allogeneic transplant is approximately 20% and the NRM for an unrelated-donor myeloablative allogeneic transplant ranges from 20-50%. In the setting of reduced-intensity conditioning and allogeneic HCT, the NRM is approximately 10% with a sibling donor and 20% with an unrelated donor.

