### **11.2 Data and Safety Monitoring Plan**

Primary internal data monitoring will be performed by the Overall Protocol Director at Stanford and site investigators and their research staff. The Protocol Director will review data to assure the validity of data, as well as the safety of the subjects. The Protocol Director will also monitor the progress of the trial. The Protocol Director will be responsible for maintaining the clinical protocol, reporting adverse event, assuring the consent is obtained and documented, reporting of unexpected outcomes and reporting the status of the trial in the continuing renewal report submitted annually to the IRB and SRC.

A safety monitoring committee (SMC) will be composed of the Protocol Director and research staff, including other site principal investigators. The SMC will conduct regular teleconferences on at least a quarterly basis or more frequent communication between the Protocol Director and research staff may occur via email or teleconference as necessary.

The data will be monitored continuously over the accrual and follow up periods by the investigators and the study coordinators. The Protocol Director will be responsible for maintaining the clinical protocol, reporting adverse event, assuring the consent is obtained and documented, reporting of unexpected outcomes and reporting the status of the trial to the IRB and the Stanford University Cancer Center Data Safety Monitoring Board (DSMB).

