### **12.4 Accrual estimates**

We performed 36 reduced-intensity allogeneic HCT for AML/ALL at Stanford in calendar year 2014. We will also plan to open this study at UCSF (with [name]) and City of Hope (with [name]). We anticipate accruing 10 to 15 subjects annually at UCSF and 20 subjects annually at City of Hope, based on their historical transplant patterns. We therefore expect that study accrual will take 1 year to complete.

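### The NRM stopping rule counts a death at once but a survivor only after a year, so at 20% NRM the chance of false termination is far above the stated 5%

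*Combined protocol and SAP*

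**What the plan says.** Section 12.2 takes a 20% cumulative incidence of NRM from a cohort conditioned with FLU/MEL as its baseline and bases the rule on NRM at 1 year. On who counts: "Patients will be evaluable with regard to the stopping rule if they die or if they reach 1 year post-transplant, whichever occurs first". On timing: "The stopping rule will be tested every increment of 5 evaluable patients". The table pairs 5, 10, 15, 20, 25, 30, 35 and 40 evaluable patients with 3, 5, 6, 8, 9, 10, 12 and 13 NRM events, introduced by "The stopping rule will be triggered if any of the following conditions are met". Crossing leads to termination and notice to FDA, with no room for judgement. The claimed performance is: "This stopping rule provides 80% power to detect an increase in NRM with a type I error rate of 0.05". The alternative NRM is not named.

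Section 12.1 sets 50 enrolled subjects. Section 12.4 says "We therefore expect that study accrual will take 1 year to complete". Section 7.2 adds that after reduced-intensity conditioning "the NRM is approximately 10% with a sibling donor and 20% with an unrelated donor". No section orders patients by transplant date for this rule or limits the count to patients with a year of potential follow-up.

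**The concern.** A boundary of this kind assumes that the first 5, 10, 15... evaluable patients are an unselected sample in which each has the baseline chance of NRM. Under the sentence above they are selected on outcome. Of two patients transplanted on the same day, one who dies at month 3 is counted at month 3, and one who lives is not counted until month 12. With a 12-month accrual, the early looks fall when only deaths can be counted. The first look then asks whether 3 of 5 deaths were non-relapse deaths, which measures the mix of causes of death and not 1-year NRM.

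Since crossing ends the study, the stated 0.05 is the only protection against closing a trial that has no excess NRM, probably before the 18-month relapse endpoint can be assessed.

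A second, smaller problem is that the table does not deliver 0.05 at 20% NRM even in an unselected sample if reaching the listed number is the trigger.

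**Working it through.** **1. The stated figures, with no selection.** Take patients in transplant order, each with independent NRM probability p, and apply an exact binomial recursion over the eight looks.

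| Trigger | p = 0.15 | p = 0.20 | p = 0.35 | p = 0.40 |
|---|---|---|---|---|
| Number reached | 0.048 | 0.148 | 0.79 | 0.92 |
| Number exceeded | 0.009 | 0.051 | 0.64 | 0.84 |

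At 20% NRM the stated 0.05 is reproduced only if the number must be exceeded; power is then 80% at an NRM of about 39%. If reaching it is enough, the table fits a null of about 15%, with 80% power at about 35%. At 20% the first look alone then has P(X ≥ 3 | n = 5) = 10(0.2³)(0.8²) + 5(0.2⁴)(0.8) + 0.2⁵ = 0.058.

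**2. When the first look happens.** Let r be the proportion dying of relapse within the year. Assume uniform entry over 12 months and uniform death times over the 12 months after transplant. Half of all deaths then fall before study month 12, so the number of deaths by then is Binomial(50, (0.20 + r)/2), with mean 50 × 0.25/2 = 6.25 at r = 5% and 50 × 0.45/2 = 11.25 at r = 25%. The chance of at least 5, so that the first look contains deaths only, is 76% to 99%.

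**3. What that look tests.** With equal timing, each death is an NRM death with probability 0.20/(0.20 + r): 0.80 at r = 5%, 0.50 at r = 20%, 0.44 at r = 25%. The chance that at least 3 of 5 are NRM is 94%, 50% and 40%, against 5.8% in an unselected sample.

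**4. The whole rule as written.** This was simulated with 20,000 to 50,000 trials per cell. There were 50 patients, 12-month accrual, true NRM 20%, mutually exclusive causes of death and no loss to follow-up. Patients were sorted by the date they become evaluable and compared with the printed table.

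| Relapse deaths | 5% | 10% | 15% | 20% | 25% |
|---|---|---|---|---|---|
| Stops, number reached | 0.911 | 0.855 | 0.787 | 0.728 | 0.663 |
| Of these, before month 12 (share of all trials) | 0.724 | 0.733 | 0.673 | 0.608 | 0.542 |
| Stops, number exceeded | 0.741 | 0.638 | 0.554 | 0.487 | 0.422 |

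**5. Sensitivity.** Relapse deaths are 5% to 25% throughout. Early timing means a density falling linearly to zero at 12 months; late timing means one rising linearly from zero.

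| Change from the base case | Reached | Exceeded |
|---|---|---|
| Early, uniform or late timing of both causes | 29% to 98% | 14% to 92% |
| Accrual over 24 to 36 months | 38% to 66% | 16% to 40% |
| True NRM 15% | 42% to 77% | 19% to 51% |
| True NRM 10% | 19% to 49% | 5% to 22% |

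With nine timing pairs and the five relapse-death levels, 40 of 45 cells exceed one half when the number need only be reached. The lowest cell has late NRM, early relapse deaths and 25% relapse deaths. If only 45 treated patients count, with deaths over months 2.5 to 12 and NRM of 15% to 20%, the range is 34% to 80% (reached).

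**The case against.** The strongest objection is that the size rests on inputs the plan does not give: the timing of NRM, the rate and timing of relapse deaths, and the null itself. Section 12.2 cites 20% without a time horizon and for FLU/MEL only, FLU/BU is also eligible, and Section 7.2 gives 10% for sibling donors. The table, read as reached, comes close to the stated 0.05 and 80% for a null of 15% against 35%. Relapse deaths above 25% also dilute the bias: at 30% to 35% the base case falls to about 59% to 53%.

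That is right as far as it goes, and the results should be quoted as ranges. It does not rescue the rule. At a 15% null the same table gives 4.8% in transplant order and 42% to 77% as written. At 20% NRM no combination tried brings the error near 5%; the most favourable timing cell under the lenient reading is still 14%. Only at a true NRM of 10%, half the named baseline, does the lenient reading reach about 5%.

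It can also be said that the plain reading of the table is that reaching the number triggers. In that case 14.8% against 5% is a calibration error separate from the counting problem, and it is kept separate above.

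Finally, the bias errs towards stopping and so does not hide harm, and the primary-endpoint power figures (84% and 78%) are unaffected. Both are true, but a rule that fires in most trials with no excess NRM cannot tell harm from baseline.

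**Conclusion.** The concern holds. That early looks contain deaths only follows from the text of Section 12.2 and needs no outside assumption; how far the error rises does. At the planned 1-year accrual and 20% NRM, with uniform timing and relapse deaths of 5% to 25%, false termination is 91% down to 66% (reached) or 74% down to 42% (exceeded), against a stated 5%. Counting in transplant order gives 14.8% or 5.1%, so most of the excess comes from the evaluability sentence and the rest, if reaching the number triggers, from the boundary. Slower accrual or a lower true NRM reduces the figure, but across the ranges tried it stays above 5% in all but the single corner noted above. The stated error and power therefore do not describe the rule as written. Because termination is automatic, this must be corrected before the rule is used.

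**What to change.** Replace the evaluability sentence so that deaths and survivors enter on the same basis. There are two workable forms.

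- **(a) Preferred: calendar looks.** At set dates, compare observed NRM deaths with the number expected from the accumulated follow-up of all transplanted patients at the 20% baseline. Section 11.2 already offers a schedule: "The SMC will conduct regular teleconferences on at least a quarterly basis". That committee consists of the Protocol Director and research staff, so the results should also go to the DSMB. As an illustration, eight quarterly looks in months 3 to 24, stopping at a one-sided Poisson p-value of about 0.02 or less, give an overall type I error of 0.05, power of 0.69 at 35% NRM and 0.88 at 40%, and stopping by month 12 in 54% of trials at 40%. This form needs a baseline NRM curve over time, not only the 20% figure. A boundary set for uniform timing has a type I error of about 0.19 if NRM is in fact front-loaded and 0.01 if it is late.
- **(b) Fallback: transplant order.** Test each block of 5 only when all its members have died or reached 1 year. This does not depend on timing, but the first look comes at about month 13 (5th to 95th percentile 12.3 to 14.0), when all 50 patients are already transplanted on the planned accrual.

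For either form, state whether the tabulated number triggers when reached or when exceeded, name the null and alternative NRM, recalibrate the boundary by simulation, and restate type I error and power. Transplant ordering alone does not restore 5% if reaching the number triggers.

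The cost is re-simulation and an amendment to Section 12.2, with no new data collection.
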